## 7. Dosage of Investigational Product

Treatment Method	Medication	Dose	Frequency
Quintuple Therapy	Hydroxychloroquine	200mg	BID
	Azithromycin	500mg \ Day 1 → 250mg Day 2-5	Daily
	Vitamin C	1500mg	BID
	Vitamin D	1500IU	BID
	Zinc	25mg	BID
Placebo	Placebo	1 tablet	BID
	Placebo	2 tablets day 1, then 1 tablet day 2-5	Daily
	Vitamin C	1500mg	BID
	Vitamin D	1500IU	BID
	Zinc	25mg	BID

## 8. Sample Collection

Samples for COVID-19 testing will be collected by the Subject using synthetic swabs with plastic shafts. Nasal or oropharyngeal swabs will be collected and immediately be placed into a sterile vial with 2-3 mL of viral transport media. These will be placed into biohazard bags, boxed up, the box sterilized, and picked up for shipment to the central laboratory. Samples will be tested by RT-PCR.

## 9. Sample Storage

Samples to be stored by the Cole Laboratories central lab for possible future testing and analysis.

## 10. Subject Injury

In the event of any untoward medical occurrence in a subject directly caused by procedures performed pursuant to this protocol, it is the responsibility of the Investigator to record all relevant information regarding the medical occurrence in the EDC and in source documents.

The Investigator is responsible for the proper reporting of any potential adverse events (AE) or serious adverse events (SAE) (as defined by general medical standards) to the appropriate medical device manufacturer related to the study. AEs/SAEs related procedures should be reported directly to the sponsor. Any malfunction of the medical devices used in this study will be reported to the manufacturer. The investigator is responsible for ensuring that adequate medical care is provided to a subject for any untoward medical occurrence resulting from this clinical protocol.

## 11. Adverse Events and Serious Adverse Events

An AE is any untoward medical occurrence in a clinical investigation participant administered a study drug, which does not necessarily have a causal relationship with this treatment. An AE can therefore be any unfavorable and unintended sign (including an abnormal laboratory finding), symptom, or disease temporally associated with the use of the study drug whether or not it is considered related to the study drug.

If the Subject has any abnormal laboratory and other abnormal investigational findings (e.g., physical examination, ECG) should not be reported as AEs unless they are associated with clinical signs and symptoms, lead to treatment discontinuation, or are otherwise considered clinically relevant by the investigator.

In cases of surgical or diagnostic procedures, the condition/illness leading to such a procedure is considered as the AE rather than the procedure itself. In the case of a fatality, the cause of death is considered as the AE, and the death is considered as its outcome.

### 11.1 Unexpected Adverse Events

An unexpected AE, the nature, severity, specificity, or outcome of which is not consistent with the summary of product characteristics described in the Product Insert

### 11.2 Events Not to be Considered an Adverse Event

Pre-existing medical conditions/signs/symptoms present 30 days prior to the Screening Period that do not worsen in severity or frequency during the study are defined as Baseline Medical Conditions, and are not to be considered AEs. Anticipated day-to-day fluctuations of pre-existing conditions, including the disease under study, that do not represent a clinically significant exacerbation or worsening need not be considered AEs.

Not to be Considered an SAE are Hospitalization for:

- A standard procedure for protocol therapy administration. However, hospitalization or prolonged hospitalization for a complication of therapy administration will be reported as an SAE.
- Routine treatment or monitoring of the studied indication not associated with any deterioration in condition.
- A procedure for protocol/disease-related investigations (e.g., surgery, scans, endoscopy, sampling for laboratory tests, bone marrow sampling). However, hospitalization or prolonged hospitalization for a complication of such procedures remains a reportable SAE.
- Hospitalization or prolongation of hospitalization for technical, practical, or social reasons, in the absence of an AE.
- A procedure that is planned (i.e., planned prior to starting of treatment on study); must be documented in the source document and the eCRF. Hospitalization or prolonged hospitalization for a complication remains a reportable SAE.
- An elective treatment of a pre-existing condition unrelated to the studied indication.
- Emergency outpatient treatment or observation that does not result in admission, unless fulfilling other seriousness criteria above.

If an AE is considered serious, both the AE page/screen of the eCRF and the SAE Report Form must be completed.

For each SAE, the investigator will provide information on severity, start and stop dates, relationship to investigation product, rationale of the causality, the action taken regarding IP, and outcome.

### 11.3 Serious Adverse Events

An SAE is any AE, occurring at any dose level/regimen and regardless of causality that:

- Results in death.
- Is life-threatening: Life-threatening means that the Subject was at immediate risk of death from the reaction as it occurred (i.e., it does not include a reaction that hypothetically might have caused death had it occurred in a more severe form).
- Requires inpatient hospitalization or prolongation of existing hospitalization; however, a hospitalization for an elective procedure will not be considered an SAE.
- Results in persistent or significant disability/incapacity. An AE is incapacitating or disabling if the experience

results in a substantial and/or permanent disruption of the subject's ability to carry out normal life functions.

- Is a congenital anomaly/birth defect: Congenital anomaly/birth defect in a child of a subject or its partner that was exposed to study drug prior to conception or during pregnancy.
- Other, is an important medical event: An important medical event is an event that may not result in death, be life-threatening, or require hospitalization but may be considered an SAE when, based upon appropriate medical judgment, it may jeopardize the Subject and may require medical or surgical intervention to prevent one of the outcomes listed in the definitions for SAEs. Examples of such medical events include allergic bronchospasm requiring intensive treatment in an emergency room or at home, blood dyscrasias, or convulsions that do not result in inSubject hospitalization, or the development of drug dependency or drug abuse.

For the purposes of reporting per regulations, any suspected transmission of an infectious agent via a medical product is by default a suspected unexpected serious adverse reaction (SUSAR) and should be reported in an expedited manner

#### **11.4 Severity**

Investigators must evaluate the severity/intensity of AEs and SAEs according to the current active version of the NCI-CTCAE, preferentially using the graded scales. If there is a change in the severity of an AE, it must be recorded as a separate event. If a particular AE's severity/intensity is not specifically graded, the investigator should apply the general guidelines for determination of Grade 1 through Grade 5 as listed in the NCI-CTCAE cover page (as shown below), using their best medical judgment:

- Grade 1: Mild; asymptomatic or mild symptoms; clinical or diagnostic observations only; intervention not indicated.
- Grade 2: Moderate; minimal, local, or noninvasive intervention indicated; limiting age appropriate-instrumental activities of daily living (preparing meals, shopping for groceries or clothes, using the telephone, managing money, etc.).
- Grade 3: Severe or medically significant but not immediately life-threatening; hospitalization or prolongation of hospitalization indicated; disabling; limiting self-care activities of daily living (bathing, dressing and undressing, feeding self, using the toilet, taking medications, and not bedridden).
- Grade 4: Life-threatening consequences; urgent intervention indicated.
- Grade 5: Death related to AE.

The term "severe" is often used to describe the intensity of a specific event (as in mild, moderate, or severe myocardial infarction); the event itself, however, may be of relatively minor medical significance (such as severe headache). This criterion is not the same as "serious," which is based on subject/event outcome or action criteria associated with events that pose a threat to a subject's life or functioning.

Seriousness, not severity, serves as a guide for defining regulatory obligations.

#### **11.5 Relationship to Study**

The investigator must determine the relationship between the administration of study drug and the occurrence of an AE/SAE as Not Suspected or Suspected as defined below. Factors for the assessment of causal relationship include, but are not limited to, the temporal relationship between the AE and the administration of study drug, known side effects of study drug, concomitant therapy, course of the underlying disease and pertinent study procedures.

- Not Suspected: Means a causal relationship of the AE to study drug administration is unlikely or remote, or other medications, therapeutic interventions, or underlying conditions provide a sufficient explanation for the observed event
- Suspected: Means there is a reasonable possibility that the administration of study drug caused the AE. "Reasonable possibility" means there is evidence to suggest a causal relationship between the study drug and the AE.

#### **11.6 Documentation and Methods of Detecting Adverse Events and Serious Adverse Events**

It is the responsibility of the investigator to document all AEs that occur during the study. Participants will be

evaluated and questioned generally for AEs during the course of the study, starting at the signing of the informed consent. Care will be taken not to introduce bias when detecting AEs and/or SAEs. Open-ended and non-leading verbal questioning of the participant is the preferred method to inquire about AE occurrences. All clearly related signs, symptoms which are either volunteered by participants or observed during or following the course of investigational product administration on the appropriate eCRF. AEs and SAEs reported from the signing of the ICF to the EOS visit are to be reported and documented on the AE eCRF. Any AE related to a protocol procedure should be marked as such on the eCRF.

All AEs spontaneously reported by the participant and/or in response to an open question from study personnel or revealed by observation, physical examination, or other diagnostic procedures will be recorded on the AE eCRF. Any clinically relevant changes in laboratory assessments or other clinical findings as are considered AEs and must be recorded on the AE eCRF. AEs are to be followed for resolution.

It is important that each AE report include a description of the event, duration (onset and resolution dates), severity, relationship with treatment, any other potential causal factors, any treatment given or other action taken (including dose modification or discontinuation of treatment), and outcome. In addition, SAEs should be identified and the appropriate seriousness criteria documented. AEs categorized as SAEs must also be documented within the appropriate SAE section in the eCRF or a paper SAE form if the system is down or otherwise unavailable. Note both methods should not be used beside each other, the paper is for back up reporting only.

#### **11.7 Documentation and Detection of Adverse Events and Serious Adverse Events**

It is the responsibility of the investigator to document all AEs that occur during the study. Participants will be evaluated and questioned generally for AEs during the course of the study, starting at the signing of the informed consent. Care will be taken not to introduce bias when detecting AEs and/or SAEs. Open-ended and non-leading verbal questioning of the participant is the preferred method to inquire about AE occurrences. All clearly related signs, symptoms which are either volunteered by participants or observed during or following the course of investigational product administration on the appropriate eCRF. AEs and SAEs reported from the signing of the ICF to the EOS visit are to be reported and documented on the AE eCRF. Any AE related to a protocol procedure should be marked as such on the eCRF.

All AEs spontaneously reported by the participant and/or in response to an open question from study personnel or revealed by observation, physical examination, or other diagnostic procedures will be recorded on the AE eCRF. Any clinically relevant changes in laboratory assessments or other clinical findings as are considered AEs and must be recorded on the AE eCRF. AEs are to be followed for resolution.

It is important that each AE report include a description of the event, duration (onset and resolution dates), severity, relationship with study drugs, any other potential causal factors, any treatment given or other action taken (including dose modification or discontinuation of study), and outcome. In addition, SAEs should be identified and the appropriate seriousness criteria documented. AEs categorized as SAEs must also be documented within the appropriate SAE section in the eCRF or a paper SAE form if the system is down or otherwise unavailable as described in Section 8.3.4. Note both methods should not be used beside each other, the paper is for back up reporting only.

### **12. Direct Access to Source Data/Documents**

The investigator involved in this study will agree to allow direct access to authorized auditors, IRB reviewers, and all applicable regulatory bodies as necessary to study relevant source data and documents including study relevant portions of the subject's medical record if necessary.

### **13. Risk/Benefit Assessment**

#### **13.1 Potential Risks**

- Confidentiality Risks: All data (clinical, demographic, etc.) for individual subjects will be provided to ProgenaBiome. Information obtained during the study will not be shared outside the study personnel except in scientific reports or publications in aggregated and deidentified form.

- Risks associated with Hydroxychloroquine
  - Auditory
    - Tinnitus
    - Hearing loss
  - Cardiovascular
    - Cardiomyopathy (can result in fatal cardiac failure)
    - biventricular hypertrophy
    - Prolongation of Q-T Interval
  - Dermatologic
    - Pigmentary changes in skin and mucous membranes
      - Usually reversible upon discontinuation of medication
    - Bleaching of hair
      - Usually reversible upon discontinuation of medication
    - Alopecia
      - Usually reversible upon discontinuation of medication
    - Rash/pruritus
    - AGEP
      - Usually reversible upon discontinuation of medication
    - Outbreak of psoriasis, occasionally associated with fever and hyperleukocytosis
    - Urticaria
    - Angioedema
    - Bullous eruptions including
      - Erythema multiforme
      - Stevens-Johnson syndrome
      - Toxic epidermal necrolysis
    - DRESS syndrome
    - Photosensitivity
    - Exfoliative dermatitis
  - Gastrointestinal
    - Abdominal pain
    - Nausea
    - Diarrhea
    - Vomiting
  - Hematologic
    - Bone marrow suppression
    - Anemia
    - Aplastic anemia
    - Agranulocytosis
    - Leukopenia
    - Thrombocytopenia
  - Hepatic
    - Fulminant hepatic failure
  - Metabolic
    - Anorexia
    - Hypoglycemia
    - Exacerbation or precipitation of porphyria
  - Musculoskeletal
    - Sensorimotor dysfunction
    - Skeletal muscle myopathy or neuromyopathy

- May be reversible by stopping medication but recovery could take months
  - Depression of tendon reflexes
  - Abnormal nerve conduction studies
- Nervous system
  - Headache
  - Dizziness
  - Seizure
  - Vertigo
  - Auditory nerve dysfunction
  - Ataxia
- Optical
  - Blurred vision
    - Dose dependent and reversible upon discontinuation of medication
  - Retinopathy with changes in pigmentation and other visual field defects
    - Subjects with retinal changes may be asymptomatic initially, or may have scotomatous vision with paracentral, pericentral ring types, temporal scotomas, and abnormal color vision.
  - Corneal changes including [edema](#) and opacities can be symptomless or may cause disturbances such as haloes, blurring of vision, or photophobia. They may be transient and are reversible when therapy is discontinued.
  - Maculopathies ,and macular degeneration (may be irreversible), extra-ocular muscle palsies (reversible), nystagmus
    - Maculopathies, and macular degeneration, can occur from 3 months to several years of exposure to this drug and may be irreversible
- Psychiatric
  - Affect lability
  - Nervousness
  - Psychosis
  - Suicidal behavior
- Respiratory
  - Bronchospasm
- Risks associated with azithromycin
  - Dermatologic
    - Generalized rash
    - Pruritis
    - Photosensitivity reaction
    - Stevens-Johnson syndrome
    - Urticaria
    - Dermatitis
    - Dry Skin
    - Hyperhidrosis
    - Eczema
    - DRESS
    - Toxic epidermal necrolysis
    - Erythema multiforme
    - Fungal dermatitis
    - Sweating
    - Vesiculobullous rash

- Maculopapular rash
- Gastrointestinal
  - Diarrhea
  - Nausea
  - Vomiting
  - Abdominal pain
  - Loose stools
  - Flatulence
  - Dyspepsia
  - Stomatitis
  - Gastroenteritis
  - Oral candidiasis
  - Constipation
  - Dysphagia/oral dysphagia
  - Abdominal distention
  - Dry mouth
  - Eructation
  - Mouth ulceration
  - Salivary hypersecretion
  - Pseudomembranous colitis
  - Pancreatitis
  - Tongue discoloration
  - Melena
  - Enteritis
  - Abnormal stools
  - Gastrointestinal disorders
  - Pyloric stenosis
- Genitourinary
  - Vaginitis
  - Vaginal infection
  - Dysuria
  - Intermenstrual bleeding
  - Testicular disorders
- Hematologic
  - Lymphopenia
  - Decreased hematocrit
  - Decreased hemoglobin
  - Neutropenia
  - Eosinophilia
  - Increased platelet count
  - Increased hematocrit
  - Increased lymphocytes
  - Increased basophils
  - Increased monocytes
  - Increased neutrophils
  - Thrombocytopenia
  - Anemia/Hemolytic anemia
  - Decreased platelet count
- Hepatic

- Hepatitis
- Increased AST, ALT, GGT, or blood bilirubin
- Hepatic failure
- Fulminant hepatitis
- Hepatic necrosis
- Hypersensitivity
  - Allergic reaction
  - Angioedema
  - Hypersensitivity
  - Anaphylactic reaction
- Immunologic
  - Moniliasis
  - Flu syndrome
- Metabolic
  - Decreased bicarbonate
  - Anorexia
  - Hyponatremia
  - Elevated alkaline phosphatase
  - Elevated bicarbonate
  - Hypochloridemia
  - Elevated lactate dehydrogenase
  - Hyponatremia
  - Hypokalemia
  - Dehydration
- Musculoskeletal
  - Arthralgia
  - Osteoarthritis
  - Myalgia
  - Back pain
  - Neck pain
  - Elevated creatinine kinase
- Nervous system
  - Headache
  - Dizziness
  - Paresthesia
  - Dysgeusia
  - Somnolence
  - Hypesthesia
  - Syncope
  - Convulsion
  - Anosmia
  - Ageusia
  - Parosmia
  - Vertigo
  - Myasthenia gravis
  - Taste perversion
  - Hyperkinesia
  - Hyperactivity
- Optical

- Visual impairment
- Conjunctivitis
- Other
  - Deafness
  - Fatigue
  - Candidiasis
  - Otic disorders
  - Aesthenia
  - Malaise
  - Facial edema
  - Pyrexia
  - Pain
  - Post-procedural complications
  - Fungal or bacterial infection
  - Mucositis
  - Fever
  - Chills
- Psychiatric
  - Nervousness
  - Insomnia
  - Agitation
  - Aggression
  - Anxiety
  - Delirium
  - Hallucination
  - Emotional lability
  - Irritability
  - Hostility
- Renal
  - Nephralgia
  - Elevated BUN and creatinine
  - Acute renal failure
  - Interstitial nephritis
- Respiratory
  - Dyspnea
  - Pneumonia
  - Pharyngitis
  - Rhinitis
  - Epistaxis
  - Bronchospasm
  - Cough
  - Pleural effusion
  - Asthma
  - Bronchitis
  - Reactive airway
- Risks associated with Vitamin C
  - Common side effects
    - Diarrhea
    - Nausea

- Vomiting
- Abdominal cramps/pain
- heartburn
- Serious side effects
  - Dysuria
  - Pink or bloody urine
  - Allergic reaction: rash, pruritis, edema (especially of the face/tongue/throat), severe dizziness, dyspnea
- Risks associated with Vitamin D
  - Common side effects
    - None
  - Serious side effects
    - Nausea
    - Vomiting
    - Constipation
    - Hypercalcemia
    - Hypercalcemia
    - Polydipsia
    - Polyuria
    - Mental status/mood changes
    - Fatigue
    - Allergic reaction: rash, pruritis, edema (especially of the face/tongue/throat), severe dizziness, dyspnea
- Risks associated with Zinc
  - Common side effects
    - diarrhea
    - Abdominal cramps
    - Vomiting
    - Anosmia
    - Metallic taste
  - Serious side effects
    - Renal damage
    - Gastropathy
    - Decreased copper absorption

### **13.2 Potential Benefits to Society**

- Successful treatment of COVID-19 could save countless lives. The value cannot be calculated

## **14. Ethical Considerations**

### **14.1 Participant Information and Informed Consent**

The Informed Consent Forms and any other related documents (including a HIPAA Authorization) must be approved by the IRB prior to study initiation. The Principal Investigator or his/her designee must obtain a signed Informed Consent Form for each subject prior to initiating any study procedure. Receipt of the signed Informed Consent Form will be documented in the CRFs and the original signed consent will be retained by the Investigator. A copy of the signed Informed Consent Form is offered to each subject. The site research staff will comply with the study protocol and will be responsible for the administration of informed consent and for acting in accord with the Health and Information Portability and Accountability Act (HIPAA) requirements. The study site is responsible for the accuracy and completeness of the data submitted and for making medical records and source documents available to the regulatory bodies.

The risks and benefits of participating in this study will be explained to each potential subject, prior to entering

into the study. The Informed Consent Form must be written in language readily understood by the subject.

## 15. Statistical analysis

The treated patients in this study will be compared to the placebo group. Measurements will include PCR test results, presence or absence of symptoms, and symptom severity. PCR results will be compared between the groups as positive or negative

In this study, the meaningful threshold will be calculated as mean change in clinical symptoms as recorded in the diary, from Day 1 through week 12. Each category in the diary will be assigned a number, 0 for None, 1 for Mild, 2 for Moderate and 3 for severe. Each category will be analyzed independently and they will be analyzed as a group. Ultimately, efficacy will be determined based upon reduction and/or progression of symptomatic days, reduction of symptom severity, as well as analysis of the subject's RT-PCR testing per protocol. These data will be compared to an existing database of de-identified Subject data.

The change of these measurements from the end to the baseline (post-pre) will be used as the primary outcome, for example,  $\mu_e = \mu_{e1} - \mu_{e0}$ , where  $\mu_{e1}$  and  $\mu_{e0}$  are the outcome of Subjects from the treatment group at the end and at baseline, respectively.

Categorical variables will be summarized by presenting the number (n) and percent (%) of subjects in each category. All Statistical tests for the analysis will be performed using the  $p < 0.05$  level of significance. All confidence intervals will be one-sided

Sample size was calculated as follows:

$$n = \frac{\log \beta}{\log \rho}$$

Where  $\beta = \text{the probability of a Type II error}$

$\rho = \text{the proportion of the population NOT affected}$

The proportion of the population affected by COVID-19 is 0.005 percent, thus 0.995 percent aren't affected

The probability of a type II error is 0.05

Thus:

$$n = \frac{\log 0.050}{\log 0.995}$$

$$n = 597.647$$

A sample size of 600 will be used

Additional details can be found in the Statistical Analysis Plan that will be developed prior to database lock.

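### Section 15 takes its meaningful threshold from the trial's own mean diary change, so the plan has no preset size of effect that counts as worthwhile

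*Combined protocol and SAP*

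**What the plan says.** All the relevant text is in Section 15 (Statistical analysis), apart from the diary schedule.

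- **Threshold:** "the meaningful threshold will be calculated as mean change in clinical symptoms as recorded in the diary, from Day 1 through week 12". No number of points is given, nor a responder definition, a between-arm margin, or the arm (or pool) over which the mean is taken.
- **Scale:** "Each category in the diary will be assigned a number, 0 for None, 1 for Mild, 2 for Moderate and 3 for severe". Diary categories are analysed both singly and together.
- **Primary outcome in this section:** end minus baseline. The only worked symbols "are the outcome of Subjects from the treatment group at the end and at baseline, respectively".
- **Comparators:** "The treated patients in this study will be compared to the placebo group", and later "These data will be compared to an existing database of de-identified Subject data". The second comparison has no defined role.
- **Basis for efficacy:** "Ultimately, efficacy will be determined based upon reduction and/or progression of symptomatic days, reduction of symptom severity", together with RT-PCR results. No numeric success criterion is attached.
- **Diary schedule:** in Section 3 (Study Procedures) and Section 6 (Schedule of Events) the last diary entries fall in the Day 15-30 block. None is listed at Month 1, 2 or 3.

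**The concern.** A threshold for a meaningful result should be a yardstick fixed outside the data. Here it is a statistic of the same diary change that Section 15 treats as the primary outcome. It therefore moves with how ill subjects were at entry, how far they recovered unaided, and how well the drugs worked. A result could be reported as reaching the meaningful threshold when that says little or nothing about clinical worth. Once data exist, the analyst could also still choose which mean to use and how to apply it.

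**Working it through.** **Inputs.** From the documents: 600 subjects, two arms, type II error 0.05, unaffected proportion 0.995, diary scale 0 to 3, last diary at Day 30. The documents give no allocation ratio, SD, expected change or important difference. I therefore assume 300 per arm, an SD of 1 point (range shown below), natural improvement r of 0.5, 1.0 or 1.5 points, and a true drug effect e of 0, 0.05, 0.1 or 0.3 points. Section 15 defines change as end minus baseline; I reverse the sign so that larger means better. T and C are the mean improvements on treatment and placebo.

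**1. The plan's own figure.** n = ln(0.05)/ln(0.995) = 597.647, rounded up to 600. This reproduces. It is the number needed to see at least one case with 95% probability at 0.5% prevalence. It contains no effect size, so no important difference can be read back from it.

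**2. Threshold = treated-arm mean.** T − T = 0 always, so the arm meets the bar by identity.

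**3. Threshold = pooled mean M.** With a share w of subjects on treatment, T − M = (1 − w)(T − C). For equal arms this is (T − C)/2. The treated arm exceeds M exactly when T is greater than C, by any amount. Hence P(pass) = Φ(e / (SD × √(2/300))), with √(2/300) = 0.0816.

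| True effect e | e / 0.0816 | P(pass) by formula | Simulated, 20,000 trials per scenario |
|---|---|---|---|
| 0 | 0 | 0.50 | 0.498 to 0.501 |
| 0.05 | 0.61 | 0.73 | 0.727 to 0.730 |
| 0.1 | 1.22 | 0.89 | 0.888 to 0.891 |
| 0.3 | 3.67 | 1.00 | 1.000 |

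The simulated ranges cover the three values of r, which make no difference. The null figure of 0.50 holds for any SD. At e = 0.1 the probability is 0.99 with an SD of 0.5 (0.1/0.0408 = 2.45) and 0.73 with an SD of 2 (0.1/0.163 = 0.61). Using the placebo mean as the bar gives the same rule, since passing again means T > C.

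**4. The bar moves.** The expected value of M is r + e/2. With e = 0 it is 0.50, 1.00 or 1.50, which is natural improvement alone. With e = 0.3 it is 0.65, 1.15 or 1.65.

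**5. Applied per subject against M.** With normal changes and SD 1, the share above M is Φ(e/2) on treatment and Φ(−e/2) on placebo. That is 0.50 and 0.50 at e = 0, and 0.56 and 0.44 at e = 0.3. The overall share stays at (0.56 + 0.44)/2 = 0.50. The arms do separate, but a responder is only someone above this sample's average.

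**6. The between-arm difference must itself reach M.** In expectation this needs e ≥ r + e/2, that is e ≥ 2r: the drug effect must be twice natural improvement. In simulation it was met in 0.000 of trials in every scenario, including e = 0.3.

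**7. What the significance test supplies.** With 300 per arm, the smallest observed difference that is significant at 0.05 is 1.960 × 0.0816 = 0.16 SD two-sided, or 1.645 × 0.0816 = 0.13 SD one-sided (Section 15 does not state sidedness for tests). This shows that a difference exists, not that it is large enough to matter.

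**8. Diary window.** Week 12 ends at Day 84 and the diary ends at Day 30, leaving 84 − 30 = 54 days without entries.

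**The case against.** The strongest reply is that the sentence is loose wording for an endpoint, mean change in diary score, and that no decision rule in Section 15 goes on to apply the threshold. That is possible, and perhaps likely. But on that reading the plan has no meaningful threshold at all, and the sentence still needs replacing.

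A second reply is that the trial is randomized and placebo-controlled, so natural recovery is common to both arms and cancels. This stands. A reader might infer from the threshold sentence that the trial cannot tell a drug effect from natural recovery. The documents do not support that: Section 15 opens with the placebo comparison and tests at the 0.05 level, and step 5 shows the arms separating even under a per-subject use of the pooled mean.

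A reader might also infer that the threshold is one the data always satisfy. That is true only if the treated arm is judged against its own mean, which Section 15 does not state. Under the pooled reading a null regimen passes about half the time, and under the reading in step 6 it almost never does.

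A third reply is that Section 15 defers detail to a Statistical Analysis Plan. That plan could hold the correction, but it need only exist by database lock, and nothing requires it to set a fixed number. Finally, the objectives tables mention an EDC symptom survey, which might run longer than the diary. No schedule for it is given, and the threshold sentence names the diary.

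**Conclusion.** The point holds, limited to the threshold. As written, the bar is derived from the data it judges, the mean used is unspecified, and under none of the readings examined does passing it show a worthwhile effect. The results range from certain passing (own mean), through about 50% under no effect (pooled or placebo mean), to practically never (difference against pooled mean). The first follows by identity, and the second needs only that the two arm means are equally likely to fall either way under the null. The probabilities at non-zero effects, the per-subject shares and the simulated failure rate depend on the assumed SD, arm sizes and natural improvement. The week 12 diary change is unobtainable under the stated schedule, whichever reading is taken. This should be fixed, but it does not invalidate the randomized comparison.

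**What to change.** Delete the threshold sentence from Section 15 and put two statements in its place, repeated in the Statistical Analysis Plan:

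- **Endpoint:** the between-arm difference in diary score change, naming the score (single category or combined) and a window the diary covers, from Day 1 to no later than Day 30.
- **Important difference:** one fixed minimum important between-arm difference on that score, set before unblinding and not computed from this trial's data. Judge the estimated difference and its confidence interval against it. As Section 15 makes all intervals one-sided, say which bound is read.

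No value is proposed, because the documents contain nothing from which one could be derived. The change takes a few lines of text and no new data collection. The downside is that the sponsor is held to a number, and a statistically significant result could fall short of it.
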